5.5 Adverse Events of Interest (AEIs)

Adverse events of interest (AEIs) are defined as clinically relevant grade 3 or 4 adverse events considered possibly, probably, or definitely related to either fostamatinib or ruxolitinib as defined by CTCAE v5.0 criteria and are not related to the underlying disease.

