	
Part B:
 
Primary Endpoint: Incidence, severity, and outcomes of AEs per NCI CTCAE v 5.0, SAEs, AEs of interest (AEIs) and laboratory abnormalities during fostamatinib and ruxolitinib treatment

	
Secondary Endpoints:
 
 1. Patients with 35% or greater reduction in spleen volume as determined by ultrasound after 12 weeks of combination therapy and end of treatment 2. Mean reduction in spleen volume as determined by ultrasound after 12 weeks of combination therapy and end of treatment 3. Patients with a 50% or greater improvement in Total Symptom Score after 12 weeks of combination therapy and at end of treatment 4. Duration of uninterrupted ruxolitinib treatment 5. Change in marrow fibrosis by WHO grading
Study Population:	Twelve adult patients of any race or ethnicity with primary or secondary myelofibrosis with severe thrombocytopenia (platelet count < 50K/microL) with intermediate or high risk disease by IPSS.
Phase:	Pilot Phase II Study
Description of Sites / Facilities Enrolling:	This study will be active at Washington University School of Medicine.
Description of Study Intervention:	Both fostamatinib and ruxolitinib are oral drugs taken twice daily on a continuous basis.
Study Duration:	2 years
Participant Duration:	48 weeks

STUDY SCHEMA

[figure not shown]
Part A:

The starting dose of fostamatinib is 100 mg twice daily (BID). After the first cycle, if no major dose related safety issue is observed and the platelet count is less than 50K/microL, then the fostamatinib dose will be increased to 150 mg BID for the next 2 cycles; otherwise the dose may be continued at 100 mg BID.

Part B:

After 3 cycles of fostamatinib monotherapy, all patients with a sustained platelet count \geq 50K/microL, will continue on the current fostamatinib dose plus ruxolitinib at the recommended dose per standard prescribing guidelines for an additional 9 cycles.

Patients who do not reach platelet count of at least 50K/microL but who achieve clinical benefit per the treating provider may continue on single agent fostamatinib for up to 12 total treatment cycles. If these patients achieve a sustained platelet count of \geq 50K/microL at any point prior to Cycle 10 Day 1, then they may be eligible to enroll in Part B of the study and continue treatment with fostamatinib and ruxolitinib for the remainder of the study.

SCHEDULE OF ACTIVITIES

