5.4 Toxicity Monitoring (Stopping Rules)

A Bayesian sequential monitoring rule will be used to protect patients from excessive toxicities (see Section 12.2 for technique details), and the table below shows the boundaries of early stopping rule. That is, an early stopping of the study due to excessive toxicities will be recommended if we observe 3 patients who experienced AEs of interest (as defined in Section 5.5) out of the first 5 patients or 4 patients who experience AEs of interest out of first 9 patients.

# Patients treated	1	2	3	4	5	6	7	8	9	10	11	12
Stop if the # AEIs \geq	N/A	N/A	N/A	N/A	3	3	3	3	4	4	4	4

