5.6 Definitions of Evaluability

All patients who receive any study treatment are evaluable for toxicity. Patients are evaluated from first receiving study treatment until a 30-day follow up after the conclusion of treatment or death.

All patients are evaluable for disease response unless they discontinue treatment prior to completion of Cycle 1 and have not had any disease assessment.

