9.1 Adverse Event Collection in the Case Report Forms

All adverse events that occur beginning with start of treatment (minus exceptions defined in Section 8.0) must be captured in the Toxicity Form. Baseline AEs should be captured on the Medical History Form.

Participant death due to disease progression should be reported on the Toxicity Form as grade 5 disease progression. If death is due to an AE (e.g. cardiac disorders: cardiac arrest), report as a grade 5 event under that AE. Participant death must also be recorded on the Death Form.

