12.2 Study Design

This is a hypothesis generating limited pilot phase II study evaluating the efficacy and safety of the use of fostamatinib as a single agent and when given in combination with ruxolitinib in patients with intermediate to high risk myelofibrosis. Previous studies with fostamatinib and ruxolitinib monotherapy indicate that toxicity will be low grade and reversible with standard treatment.

This study consists of two parts. For Part A, patients with MF and severe thrombocytopenia will initially receive 12 weeks of single agent fostamatinib and the primary endpoint will be platelet response (defined as platelet count of $\geq 50K/\text{microL}$ as two separate measurements at least two weeks apart) at the end of the 12 week treatment period. Patients who achieve a sustained platelet response will then be eligible to proceed to Part B of the study and begin treatment with ruxolitinib while continuing to take fostamatinib. For Part B, patients will continue treatment with fostamatinib and ruxolitinib for up to an additional 36 weeks and the primary endpoint will be safety as assessed by NCI CTCAE v 5.0. Patients who do not have a sustained platelet response after 12 weeks of treatment but are clinically benefiting from fostamatinib may remain on Part A of the study and be eligible to enroll in Part B if they achieve a sustained platelet response prior to Day 1 Cycle 10 of treatment.

A maximum of 12 patients will be enrolled. A Bayesian sequential monitoring rule will be implemented for safety.

Safety monitoring (Part B): The stopping rule is defined as $\text{Pr}(\theta > \theta_T | \text{data}) > 0.8$, where θ denotes the proportion of AEs of interest as defined in Section 5.5 and θ_T denotes the rate of AEs of interest under the null hypotheses (i.e., 20% AEs of interest). That is, an early termination of the study due to excessive toxicities will be recommended whenever, given the accumulated observed data, there is high chance (i.e., >80% probability) for the “true” AEs of interest rate >20%. The stopping boundaries were obtained using Multc99 version 2.1, a free-download software from M.D. Anderson Cancer Center. Specifically, we assume that the parameter θ follows a prior distribution of beta (0.2, 0.8), i.e., θ with mean = 0.2 but with relatively large variability (non-informative prior). Early stopping will be recommended if we observe 3 patients who experience AEs of interest out of first 5 patients

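### Adverse events of interest stop at grade 4, so a patient whose only qualifying event is a treatment-related death is not counted by the stopping rule

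*Combined protocol and SAP*

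**What the plan says.** Section 5.5 limits AEIs to "clinically relevant grade 3 or 4 adverse events considered possibly, probably, or definitely related to either fostamatinib or ruxolitinib", and further requires that the event not be related to the underlying disease.

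Both statements of the stopping rule import that definition. Section 5.4 recommends stopping on "3 patients who experienced AEs of interest (as defined in Section 5.5) out of the first 5 patients", or on 4 of the first 9. Section 12.2 says that the monitored parameter θ is "the proportion of AEs of interest as defined in Section 5.5".

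Grade 5 is a separate category in this protocol. Section 9.1 instructs: "If death is due to an AE (e.g. cardiac disorders: cardiac arrest), report as a grade 5 event under that AE". Section 5.6 puts every treated patient in the safety denominator: "All patients who receive any study treatment are evaluable for toxicity".

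No section adds grade 5 events to the AEI count, and none sets a separate numerical rule for deaths. Fatal events do remain in the Part B primary endpoint, which the Synopsis gives as "Incidence, severity, and outcomes of AEs per NCI CTCAE v 5.0, SAEs, AEs of interest (AEIs) and laboratory abnormalities".

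**The concern.** Section 5.4 says the rule exists to protect patients from excessive toxicity. As worded, it counts a related grade 3 event but not a related death. A patient who dies of a drug-related event with no separately recorded related grade 3 or 4 event adds one to the number treated and nothing to the number of AEIs, which lowers the posterior probability of excess toxicity. The rule could then fail to recommend stopping because part of the severe toxicity was fatal. The AEI rate reported at the end would omit the same patients.

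The gap is narrow. A patient with a separate related grade 3 or 4 event before a fatal one is already counted. Deaths from disease progression, which Section 9.1 codes as grade 5 disease progression, are outside the definition on relatedness and are not at issue.

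**Working it through.** **Inputs.** From Section 12.2: prior Beta(0.2, 0.8), reference rate 20%, posterior cut-off 0.8, maximum 12 patients, and stated chances of stopping of 4% at a true rate of 10% and 76% at 40%. From the table in Sections 5.4 and 12.2: stop at 3 or more AEI patients for n = 5 to 8, and at 4 or more for n = 9 to 12.

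**Step 1: reproduce the boundaries.** With x AEI patients among n, the posterior is Beta(0.2 + x, 0.8 + n − x), and the rule stops when Pr(θ > 0.2) exceeds 0.8. The smallest qualifying x is 3 for n = 5 to 8 and 4 for n = 9 to 12, which matches the table.

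**Step 2: reproduce the stated operating characteristics.** Let X₈ be the count after 8 patients and p the true rate. The count cannot fall, so a stop at any look from n = 5 to 8 is the event X₈ ≥ 3. A stop at n = 9 to 11 then requires X₈ ≤ 2 and a total of at least 4 by n = 11. With Bin(3, p) the count among patients 9 to 11:

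Pr(stop) = Pr(X₈ ≥ 3) + Pr(X₈ = 2)·Pr(Bin(3, p) ≥ 2) + Pr(X₈ = 1)·Pr(Bin(3, p) = 3)

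- p = 0.40: 0.6846 + 0.2090 × 0.352 + 0.0896 × 0.064 = 0.764 (plan: 76%).
- p = 0.10: 0.0381 + 0.1488 × 0.028 + 0.3826 × 0.001 = 0.043 (plan: 4%).

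The plan's figures therefore correspond to looks at n = 5 to 11. Adding the printed look at n = 12 gives 81.1% and 4.7%.

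**Step 3: the effect of one uncounted death at a boundary.**

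| Patients with a related grade 3–5 event | Count as written (one is death-only) | Pr(θ > 0.2) | Count with grade 5 | Pr(θ > 0.2) |
|---|---|---|---|---|
| 3 of first 5 | 2 | 0.797, no stop | 3 | 0.960, stop |
| 4 of first 9 | 3 | 0.785, no stop | 4 | 0.934, stop |

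At the extreme, if all three affected patients among the first five were death-only, the count as written would be 0/5, with posterior 0.038.

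**Step 4: the average effect.** The documents give no related-death rate, so the shares below are assumptions. Take a true related grade 3 to 5 rate of 40%. If d percentage points of patients have death as their only qualifying event, the rule as written sees a rate of 40% − d.

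| d (points) | Rate seen | Pr(stop), looks 5–11 | Pr(stop), looks 5–12 |
|---|---|---|---|
| 0 | 40% | 76.4% | 81.1% |
| 1 | 39% | 74.3% | 79.2% |
| 2 | 38% | 72.2% | 77.1% |
| 4 | 36% | 67.5% | 72.7% |
| 10 | 30% | 51.8% | 56.9% |

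**The case against.** The strongest reply is that the practical effect is likely to be small. Section 12.2 expects low-grade, reversible toxicity. Section 1.4.5.1 describes the ITP adverse reactions as reversible, and Section 1.4.5.3 attributes the two AIHA deaths to underlying conditions. If death-only patients make up 1 or 2 points, the chance of seeing even one among 12 is 1 − 0.99¹² = 11% or 1 − 0.98¹² = 22%, and the loss of 2 to 4 points in stopping probability is no larger than the gap of about 5 points between the two look conventions. This stands: the 4- and 10-point rows show sensitivity and are not forecasts.

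Second, the scope of the rule is unclear. Section 12.2 labels it as Part B monitoring, while Section 5.4 speaks of the whole study. If only Part B patients count and entry follows the 20% or 40% response rates used as examples in Section 12.4, the chance of reaching five patients is about 7% or 56% (binomial, n = 12; later entry, before Cycle 10, could raise it). The averages in Step 4 would then not apply as given. The definition would still omit deaths.

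Third, deaths do not go unseen. Unexpected fatal suspected reactions go to the FDA within 7 days (Section 7.1.4), deaths from unanticipated problems go to the IRB within 1 working day (Appendix E), serious toxicities are monitored continuously (Section 11.0), and the center may close the study (Section 5.10). The rule itself only recommends. These are real safeguards, but none feeds the count or replaces it with another number.

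Finally, any sensible investigator would probably count a related death. That is likely the intent, but the rule should not depend on readers departing from its definition.

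**Conclusion.** The point holds and should be fixed. Under Sections 5.4, 5.5, 9.1 and 12.2 as written, a patient whose only qualifying event is a related death counts as a patient without toxicity. A single such patient can change the recommendation, at 3 of 5 or at 4 of 9. That result needs only the protocol's own prior, reference rate and cut-off.

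The average loss rests on assumed death shares, a 40% true rate and all 12 treated patients feeding the rule. It is 2 to 4 percentage points of stopping probability if such deaths are rare (1 to 2 points) and about 25 points at an assumed 10-point share. Confidence is high on the wording and its effect at the boundary; the practical size cannot be settled from the documents. The defect does not reach the collection or reporting of deaths, or the Part B primary endpoint as a whole.

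**What to change.** In Section 5.5, define AEIs as related events of grade 3 or higher (grades 3, 4 and 5), keeping the conditions on clinical relevance, relatedness and the underlying disease. Sections 5.4 and 12.2 take up the change through their cross-references.

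The cost is one line of text. The boundary table depends only on n, the prior, the 20% reference rate and the 0.8 cut-off, so it stands, as do the stated 4% and 76%, provided the 20% rate is kept. The sponsor should confirm that 20% remains the intended reference for grades 3 to 5. No new data are needed, because Section 9.1 already records grade 5 events on the Toxicity Form. Sections 5.3 and 6.1 also use AEIs, but only for later cycles in the same patient, so adding grade 5 does not affect them.

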1.3 Thrombocytopenia in MF and rationale for SYK inhibition

Thrombocytopenia is a hematologic complication of MF resulting from ineffective erythropoiesis as well as hypersplenism in the setting of splenomegaly. There are currently few effective therapies for the treatment of thrombocytopenia in MF. Treatment with ruxolitinib can further lower the platelet count, leading to dose attenuations that may limit the efficacy or prohibit continuation of the medication. Ruxolitinib (as well as Fedratinib) are also not recommended for patients with platelets < 50,000/microL, thereby limiting the treatment options for patients with MF with severe thrombocytopenia.

Fostamatinib is an oral spleen tyrosine kinase (SYK) inhibitor recently approved for the treatment of chronic idiopathic thrombocytopenic purpura (ITP), and may be a potential therapeutic option for patients with MF with severe thrombocytopenia. As hypersplenism from splenomegaly can be a contributing factor to thrombocytopenia in MF, an agent that blocks spleen tyrosine kinase signaling may improve the platelet count in these patients. Additionally, increasing the platelet count $\geq 50,000/\text{microL}$ would allow patients with severe thrombocytopenia to be treated with ruxolitinib. Another feature of fostamatinib is that there was no reported increased risk of thrombosis in the phase 3 studies [29], which makes it an attractive agent for patients with MF where thrombosis is a concern.

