5.3 Study Intervention Administration

In Part A of the study, patients will initially receive fostamatinib single agent at a starting dose of 100 mg PO twice daily (BID) for three cycles (12 weeks). Each cycle is 28 days (4 weeks).

Patients who tolerate single agent fostamatinib and achieve a sustained platelet count of $\geq 50,000/\text{microL}$ on at least two separate measurements taken at least two weeks apart at any point before Cycle 10 Day 1 will be eligible to proceed to Part B of the study and initiate treatment with ruxolitinib (starting dose will be determined by platelet count as per package insert).

For patients who do not achieve a sustained platelet count of $\geq 50,000/\text{microL}$ following the first cycle (4 weeks) of fostamatinib 100 mg BID and no AEIs (see Section 5.5) are reported, then the dose of fostamatinib may be increased to 150 mg BID and continued for subsequent cycles. If a platelet count of $\geq 50,000/\text{microL}$ is not achieved after three cycles of fostamatinib, but the patient is achieving clinical benefit, then the patient may continue on fostamatinib monotherapy for up to a total of 12 cycles of treatment and may continue

on to Part B of the study if they achieve a sustained platelet count of $\geq 50,000/\text{microL}$ by Cycle 10 Day 1. If the patient is not achieving clinical benefit or has evidence of disease progression, then the patient will be taken off study.

For Part B of the study, patients will continue on treatment with fostamatinib for up to an additional nine cycles (36 weeks) to complete a total treatment duration of 48 weeks. Ruxolitinib will be initiated in combination with fostamatinib at the start of Part B unless the patient is experiencing progressive MF symptoms and is eligible to initiate ruxolitinib, in which case ruxolitinib may be initiated sooner at the discretion of the PI. If the platelet count decreases to $< 50,000/\text{microL}$ following initiation of ruxolitinib, then the dose of fostamatinib may be increased to 150 mg BID if the patient is on the 100 mg BID dose.

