or 4 patients who experience AEs of interest out of first 9 patients. A simulation study was also performed to assess the operating characteristics for the above stopping rule (all scenarios are based on 10,000 simulated trials). If the “true” AEs of interest rate is 10%, there will be only 4% chance to stop. In contrast, we will have 76% chance to stop if the “true” rate is 40%.

# Patients treated	1	2	3	4	5	6	7	8	9	10	11	12
Stop if the # AEIs \geq	N/A	N/A	N/A	N/A	3	3	3	3	4	4	4	4

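### The AEI definition in Section 5.5, read literally, leaves out grade 3–4 events to which both a study drug and myelofibrosis contribute, so the stopping rule can lose a substantial part of its protection

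*Combined protocol and SAP*

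**What the plan says.** Section 5.5 defines an AEI as a clinically relevant grade 3 or 4 event that is "considered possibly, probably, or definitely related to either fostamatinib or ruxolitinib as defined by CTCAE v5.0 criteria and are not related to the underlying disease". Both conditions must be met. No other section says how to classify an event with more than one cause.

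The term is used in two places:

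- **Stopping rule (Sections 5.4 and 12.2).** Stopping is recommended at 3 or more patients with an AEI when 5 to 8 have been treated, and at 4 or more when 9 to 12 have been treated. The boundary comes from a Beta(0.2, 0.8) prior, a reference AEI rate of 20% and a posterior probability above 0.8. Section 12.2 gives a 4% chance to stop at a true AEI rate of 10%. At 40% it says "we will have 76% chance to stop".
- **Fostamatinib dose increase after Cycle 1 (Sections 5.3 and 6.1).** Section 5.3 makes this conditional on the finding that "no AEIs (see Section 5.5) are reported".

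On the causes of cytopenia, Section 1.3 says "Thrombocytopenia is a hematologic complication of MF resulting from ineffective erythropoiesis", and of the second drug, "Treatment with ruxolitinib can further lower the platelet count". Section 1.2 describes JAK2 inhibitors as myelosuppressive. Section 1.4.5.1 lists neutropenia as a fostamatinib reaction (6% overall, 1% severe), and Section 1.4.5.4 reports cytopenias with fostamatinib in lymphoma and solid tumors.

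**The concern.** An event rated only possibly related to a drug may already have another contributor. Adding the condition that it is unrelated to the disease then removes every event that the drug and MF share. In this trial such sharing is expected: every patient enters with platelets below 50,000/microL, and the protocol itself expects platelets to fall in some patients after ruxolitinib starts (Sections 5.3 and 6.1). An investigator who sees a grade 3–4 cytopenia on the combination may judge it possibly due to ruxolitinib and yet be unable to call it unrelated to MF. Taken at its word, Section 5.5 would not count it. The same applies to a bleed or an infection that follows from such a cytopenia.

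The boundaries are low (3 of 5, 4 of 9), so the classification of one patient can decide whether a stop is recommended. Safety of the combination is the primary objective of Part B.

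**Working it through.** **Inputs.** From Sections 5.4 and 12.2: boundary b = 3 at n = 5–8 and b = 4 at n = 9–12; prior Beta(0.2, 0.8); reference rate 20%; threshold 0.8; stated chances to stop of 4% and 76%. Assumed, because the documents give no value: f, the share of patients with a drug-related grade 3–4 event whose only such events are also judged disease-related.

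**Step 1: the boundary.** With x AEI patients among n, the posterior is Beta(0.2 + x, 0.8 + n − x). The probability that the rate exceeds 20% is 0.797 at 2 of 5 and 0.960 at 3 of 5, then 0.785 at 3 of 9 and 0.934 at 4 of 9. The printed boundary is correct at every n from 5 to 12.

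**Step 2: the stated chances to stop.** Let p be the counted rate and q = 1 − p. An early stop can occur after patients 5 to 11. The probabilities of first crossing are:

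| n | Formula | p = 0.40 | p = 0.30 | p = 0.20 | p = 0.10 |
|---|---|---|---|---|---|
| 5 | 10p³q² + 5p⁴q + p⁵ | 0.3174 | 0.1631 | 0.0579 | 0.0086 |
| 6 | 10p³q³ | 0.1382 | 0.0926 | 0.0410 | 0.0073 |
| 7 | 15p³q⁴ | 0.1244 | 0.0972 | 0.0492 | 0.0098 |
| 8 | 21p³q⁵ | 0.1045 | 0.0953 | 0.0551 | 0.0124 |
| 9 | 0 (cannot go from 2 to 4) | 0 | 0 | 0 | 0 |
| 10 | 28p⁴q⁶ | 0.0334 | 0.0267 | 0.0117 | 0.0015 |
| 11 | 64p⁴q⁷ | 0.0459 | 0.0427 | 0.0215 | 0.0031 |
| Sum, before rounding of terms | | **0.764** | **0.518** | **0.236** | **0.043** |

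The plan's 4% and 76% are reproduced. Counting a crossing at patient 12, when nothing is left to stop, would give 4.7% and 81.1%, so looks at 5 to 11 are the version that matches.

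**Step 3: leaving out mixed-cause events.** The boundary counts patients, so a patient drops out only if every qualifying event is mixed. The counted rate is 0.40 × (1 − f).

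| f (assumed) | Counted rate | Chance to stop |
|---|---|---|
| 0 | 40% | 76% |
| 10% | 36% | 68% |
| 20% | 32% | 57% |
| 25% | 30% | 52% |
| 30% | 28% | 46% |
| 40% | 24% | 35% |
| 50% | 20% | 24% |

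Half of 76.4% is 38.2%. Interpolating between f = 30% (46.1%) and f = 40% (34.6%) gives 30% + 10% × (46.1 − 38.2)/(46.1 − 34.6) ≈ 37%.

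**Step 4: the Section 12.4 figure.** The chance of at least one AEI in 12 patients at a true rate of 20% is 1 − 0.8¹² = 93%, as stated. With f = 25% it is 1 − 0.85¹² = 86%; with f = 50% it is 1 − 0.9¹² = 72%.

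**The case against.** Four objections deserve an answer.

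- **The figures are right for AEIs as defined.** Section 12.2 ties its rate to Section 5.5, and 4% and 76% reproduce. This stands. The issue is what the counted rate captures.
- **Much of the expected toxicity is unaffected.** Section 1.4.5.5 names diarrhea, hypertension, nausea and raised transaminases as the most frequent fostamatinib reactions. Nothing in the documents ascribes these to MF, severe neutropenia was 1% in the ITP trials, and a patient with any one other qualifying event still counts. This also stands. A reader might infer that the rule is blind to the likely toxicities, and the documents do not support that.
- **The clause may be meant to exclude only events explained by the disease alone.** Part B entry needs a sustained count of at least 50,000/microL, so a later fall has a temporal link to ruxolitinib and some investigators would count it. That is possible, but Section 5.5 does not say so. If it is the intent, the change below only writes it down.
- **Other safeguards exist.** Part B's primary endpoint covers adverse events without the disease exclusion (Section 2.2). Adverse events are recorded whatever their cause (Section 7.0), their rates are reported with exact intervals (Section 12.3), and toxicity is monitored continuously with semi-annual reports (Section 11.0). Overlapping cytopenias would therefore be visible in the data. None of these replaces the numerical stopping rule.

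**Conclusion.** The point holds as a defect in a stated safety rule. The literal definition undercounts toxicity shared by drug and disease, no other section corrects it, and the change needed is small. It should be made.

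The size depends on an assumption. At a true drug-related rate of 40%, the chance to stop is about 68%, 52% or 24% if 10%, 25% or 50% of affected patients have only mixed-cause events, against 76% if none do. This assumes that sites apply the clause literally, that patients are independent, and that looks are made after patients 5 to 11.

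A reader might infer that the rule loses most of its protection. That would need f above about 37%, and the documents give no value for f. The supported statement is that the loss can be substantial.

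**What to change.** 1. In Section 5.5, replace the final condition with: *and are not attributable solely to the underlying disease*. A grade 3–4 event at least possibly related to either drug then counts even when MF contributes.
2. For the stopping rule, count a cytopenia only if it is worse than the grade before the relevant drug was started: before fostamatinib in Part A, before ruxolitinib in Part B. Entry thrombocytopenia is then not itself an AEI. A single baseline before fostamatinib would not do, because it would miss a responder whose platelets fall back to the entry grade on ruxolitinib.
3. Confirm that the 20% reference rate is meant for this definition. If it is, the boundary table and simulation need no change.
4. Sections 5.3 and 6.1 use the same term as a condition for the dose increase. The sponsor should reconcile those passages with the revised definition. No dosing rule is proposed here.

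**Cost.** One phrase, one counting rule for cytopenias, and a cross-check of two sections. More events will count, so stop recommendations become more likely: if the counted rate goes from 10% to 20%, the chance to stop rises from 4% to 24%. That is a real increase, and it is why item 3 is needed.
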